3.7. Dose Escalation Stopping Criteria

The study will be halted if 1 or more subject experience a serious adverse event (SAE) that is considered to be related to IMP or 2 or more subjects in the same group experience severe AEs that are considered to be related to IMP. If, following an internal safety review, the sponsor deems it appropriate to restart the study, this can be done following approval of a substantial protocol amendment. Dosing of subjects, including any ongoing multiple-dose groups, will be stopped immediately if any of the dose escalation stopping criteria are met.

In Part A and Part B, following consultation with the sponsor, dose escalation will stop if:

- Clinically relevant signs or symptoms of similar nature occur in 2 or more subjects in a group that, in the opinion of the investigator, warrant stopping of dose escalation.
- There is evidence of clinically significant increases in liver function tests defined as 3 times the upper limit of normal (ULN) for aspartate aminotransferase (AST), ALT, ALP, or gamma-glutamyl transferase (GGT) or 2 times the ULN for total bilirubin in 2 or more subjects in a group (confirmed with repeat testing).
- Moderate nausea or vomiting that prevents subjects from eating a meal on 3 or more occasions on 2 consecutive days in 2 or more subjects in a group.
- The systemic exposure for any individual subject is predicted to exceed an AUC₀₋₂₄ of 358,000 ng·hr/mL (based on the female cynomolgus monkey at the intermediate dose level of 175 mg/kg/day at Day 28) in the 28-day oral toxicity study and/or a C_{max} of 59,100 ng/mL (based on the female cynomolgus monkey kinetics at the NOAEL [350mg/kg/day at Day 28]).

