10. APPENDICES

Appendix 1: Adverse Event Reporting

Definitions

An adverse event (AE) is any untoward medical occurrence in a patient or clinical investigation subject administered a pharmaceutical product, which does not necessarily have a causal relationship with this treatment. An AE can therefore be any unfavourable and/or unintended sign (including a clinically significant abnormal laboratory finding), symptom, or disease temporally associated with the use of a study treatment, whether or not related to the study treatment.

Assessment of Severity

The investigator will be asked to provide an assessment of the severity of the AE using the following categories:

- **Mild:** Usually transient and may require only minimal treatment or therapeutic intervention. The event does not generally interfere with usual activities of daily living.
- **Moderate:** Usually alleviated with additional specific therapeutic intervention. The event interferes with usual activities of daily living, causing discomfort but poses no significant or permanent risk of harm to the subject.
- **Severe:** Interrupts usual activities of daily living, or significantly affects clinical status, or may require intensive therapeutic intervention.

Relationship to Study Treatment

The investigator (or designee) will make a determination of the relationship of the AE to the study treatment using a 2-category or binary approach system according to the following guidelines:

- **Not Related:** The AE is definitely caused by the subject's clinical state or the study procedure/conditions.
- **Related:** The AE follows a reasonable temporal sequence from administration of the drug, abates upon discontinuation of the drug, follows a known or hypothesised cause-effect relationship, and (if appropriate) reappears when the drug is reintroduced.

Follow-up of Adverse Events

Every reasonable effort will be made to follow up with subjects who have AEs. Any subject who has an ongoing AE that is related to the investigational medicinal product (IMP) or study procedures at the follow-up visit will be followed up, where possible, until resolution or until the unresolved AE is judged by the investigator (or designee) to have stabilised. This will be completed at the investigator's (or designee's) discretion. Any subject who has an ongoing AE that is not related to the IMP or study procedures at the follow-up visit can be closed out as ongoing at the investigator's discretion.

Adverse Drug Reactions

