All noxious and unintended responses to an IMP (ie, where a causal relationship between an IMP and an AE is at least a reasonable possibility) related to any dose should be considered adverse drug reactions.

For marketed medicinal products, a response to a drug which is noxious and unintended and which occurs at doses normally used in man for prophylaxis, diagnosis, or therapy of diseases or for modification of physiological function is to be considered an adverse drug reaction.

An unexpected adverse drug reaction is defined as an adverse reaction, the nature or severity of which is not consistent with the applicable product information (eg, Investigator's Brochure [IB] for an unapproved IMP).

Serious Adverse Events

A serious adverse event (SAE) is defined as any untoward medical occurrence that at any dose either:

- results in death
- is life-threatening
- requires inpatient hospitalisation or prolongation of existing hospitalisation
- results in persistent or significant disability/incapacity (disability is defined as a substantial disruption of a person's ability to conduct normal life functions)
- results in a congenital anomaly/birth defect
- results in an important medical event (see below).

Important medical events that may not result in death, be life-threatening, or require hospitalisation may be considered SAEs when, based upon appropriate medical judgement, they may jeopardise the subject and may require medical or surgical intervention to prevent one of the outcomes listed in this definition.

Instances of death or congenital abnormality, if brought to the attention of the investigator at any time after cessation of the study treatment and considered by the investigator to be related to the study treatment, will be reported to the sponsor.

Definition of Life-threatening

An AE is life-threatening if the subject was at immediate risk of death from the event as it occurred (ie, does not include a reaction that might have caused death if it had occurred in a more serious form). For instance, drug-induced hepatitis that resolved without evidence of hepatic failure would not be considered life-threatening even though drug-induced hepatitis can be fatal.

Definition of Hospitalisation

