## **8.6. Safety and Tolerability Assessments**

### **8.6.1. Adverse Events**

All AEs will be coded using the Medical Dictionary for Regulatory Activities (MedDRA) Version 24.0 (or higher if a new version is issued during the study; see the DMP for more details).

A treatment-emergent adverse event (TEAE) will be defined as an AE that starts during or after the first dose, or starts prior to the first dose and increases in severity after the first dose.

A treatment-related TEAE will be defined as a TEAE with a relationship of related to the study treatment, as determined by the investigator.

All AEs will be listed. In addition to the data recorded in the database, the listings will include derived onset time and duration. Onset time will be calculated from the time of the last associated dose for TEAEs only. Where the last associated dose is referring to the last dose received prior to the start of a TEAE.

The frequency of subjects with TEAEs and the number of TEAEs will be summarised for the following categories:

- TEAEs (overall, serious, leading to discontinuation, and leading to death) by treatment
- TEAEs by severity and treatment
- Treatment-related TEAEs (overall, serious, leading to discontinuation, and leading to death) by treatment
- Treatment-related TEAEs by severity and treatment

The frequency of subjects will be summarised separately for TEAEs and treatment-related TEAEs by the following:

- System organ class, preferred term, and treatment
- Preferred term and treatment

For the AE data the following rules will apply:

- For the derivation of treatment-emergent status (applicable to all AEs): If the start date/time of an AE is incomplete or missing, an AE will be assumed to not be a TEAE, unless the incomplete start date/time or the end date/time indicates an AE started after the first dose.
- For the derivation of treatment-related status (applicable to TEAEs only): If the study treatment relationship for a TEAE is missing, a TEAE will be assumed to not be a treatment-related TEAE.

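### The two causality categories in Appendix 1 leave a gap and conflict with its own adverse-reaction threshold, which affects the treatment-related TEAE summaries and the relatedness limbs of the halting rule

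*Protocol*

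**What the plan says.** Protocol Appendix 1 (Relationship to Study Treatment) has the investigator judge causality "using a 2-category or binary approach system according to the following guidelines". The two categories are:

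- **Not Related** is reserved for one situation: "The AE is definitely caused by the subject's clinical state or the study procedure/conditions". This sets the bar at certainty of another cause.
- **Related** is a list of features. It covers an event that "follows a reasonable temporal sequence from administration of the drug, abates upon discontinuation of the drug, follows a known or hypothesised cause-effect relationship", with reappearance on reintroduction added where appropriate.

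The Adverse Drug Reactions paragraph of the same appendix uses another threshold. It counts responses to the product "where a causal relationship between an IMP and an AE is at least a reasonable possibility".

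The category is then used in three places:

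- **Protocol Section 3.7:** "The study will be halted if 1 or more subject experience a serious adverse event (SAE) that is considered to be related to IMP". The second limb halts the study when 2 or more subjects in one group have severe AEs considered related.
- **Protocol Section 5.4:** unblinding to support dose-escalation decisions is tied to treatment-related SAEs or severe AEs.
- **SAP Section 8.6.1:** "A treatment-related TEAE will be defined as a TEAE with a relationship of related to the study treatment", as judged by the investigator. A TEAE with no recorded relationship is counted as not treatment-related.

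**The concern.** A binary scale works only if every event falls in one category or the other. Here Not Related is set at certainty of another cause, while Related is a joint list. The space between them holds the events that matter most in a first-in-human study: those with plausible timing and an unsettled cause.

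No rule says where such an event goes. Appendix 1 does give a default for doubt about hospitalisation (treat the event as serious) but none for causality. The only causality default in either document is the SAP rule for a missing relationship, and it runs towards not related.

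An error is possible in both directions. Applying the Related list strictly could leave a drug-caused SAE outside the halting rule. Treating everything not certainly due to another cause as Related could halt the study on events the drug did not cause. Either way, readers of the treatment-related tables would not know which standard the counts reflect.

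**Working it through.** The documents state no figure on this point, so there is none to reproduce. The check is a comparison of texts.

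**1. Is the Related list joint?** Its last part reads "follows a known or hypothesised cause-effect relationship, and (if appropriate) reappears when the drug is reintroduced". The qualifier sits on rechallenge only. Timing, abatement and mechanism carry no such relief, so the literal reading requires all three.

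**2. Are the categories exhaustive?**

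| Event | Not Related? | Related, read literally? | Adverse-reaction threshold? |
|---|---|---|---|
| Plausible timing, resolves, no known or hypothesised mechanism, other cause possible but not certain | No | No (mechanism) | Can be met |
| Plausible timing and mechanism, fatal or permanent, other cause not certain | No | No (abatement) | Can be met |
| All listed elements present | No | Yes | Met |
| Another cause certain | Yes | No | Not met |

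The first two rows fit neither category, yet each can be an adverse drug reaction under the same appendix.

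**3. Does Appendix 1 itself treat abatement as necessary?** No. Its follow-up paragraph provides for product-related AEs still ongoing at the follow-up visit, which Section 3.1 places 10 to 14 days after the final dose. Its SAE paragraph provides for deaths and congenital abnormalities that the investigator judges related. Both are related events that have not abated. The list is therefore inconsistent with the text around it.

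**4. What does and does not depend on the category?**

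- Independent: the primary AE endpoint (Protocol Section 2.2.1, SAP Section 3.1), which is incidence and severity of all AEs; the overall TEAE tables; the Section 3.7 criteria on similar signs or symptoms, liver tests, nausea or vomiting, and exposure; the termination grounds in Section 4.6; and SAE reporting within 24 hours.
- Dependent: both halting limbs in Section 3.7, unblinding for dose decisions in Section 5.4, and the treatment-related TEAE summaries in SAP Section 8.6.1.

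**5. How sensitive is the halting rule to classification?** This is an illustration only. Both inputs are assumptions with no source in the documents: *p* is the per-subject probability of a truly drug-caused event, and *s* is the probability that such an event is classed Related. For a group with *n* active subjects (6 in Part A, 8 in Part B) and *q = p × s*:

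P(at least 1) = 1 − (1 − q)^n

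P(at least 2) = 1 − (1 − q)^n − n·q·(1 − q)^(n−1)

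With n = 8, p = 0.10 and s = 0.5, q = 0.05, and P(at least 1) = 1 − 0.95^8 = 0.337. Results at p = 0.10:

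| n | s | SAE limb (≥1) | Severe-AE limb (≥2) |
|---|---|---|---|
| 8 | 1 | 0.570 | 0.187 |
| 8 | 0.5 | 0.337 | 0.057 |
| 8 | 0.25 | 0.183 | 0.016 |
| 6 | 1 | 0.469 | 0.114 |
| 6 | 0.5 | 0.265 | 0.033 |
| 6 | 0.25 | 0.141 | 0.009 |

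For p from 0.05 to 0.20 with n = 8, the SAE limb runs from 0.337 to 0.832 at s = 1 and from 0.183 to 0.570 at s = 0.5. The halting probability falls as s falls, but nothing in the documents says what s is.

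**The case against.** The definitions are offered as guidelines for a judgement. Section 7.2.1 records the investigator's opinion, Section 3.7 speaks of events considered related, and SAP Section 8.6.1 defers to the investigator. A hypothesised mechanism is a low bar, and the reasonable-possibility wording is in the same appendix, so a sensible assessor may read the two together. This is a single-site study, and no disagreement between assessors has been shown. The safeguards that do not use causality are real, and all available data are reviewed before each escalation (Section 3.6). Section 1.6.1.2 reports no severe or serious AEs in the 70 subjects dosed at that point, so the halting rule had not been tested.

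Most of this stands and limits the consequence. It does not close the gap: no text tells the assessor to let the lower threshold govern, and the SAE limb is meant to act on a single related event.

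Three stronger readings are tempting, and the documents do not support them:

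- **That 54 of 89 AEs (61%) judged not related measures the problem.** It shows only that assessors chose a category. Nothing shows that any of the 54 was misclassified or fitted neither definition.
- **That the 40 of 70 subjects (57%) dosed in Part A are affected.** This counts subjects, including those on placebo, not AEs.
- **That abatement cannot be judged after a single dose.** Section 1.6.1.1 gives half-lives of roughly 1 to 3 hours, so an assessor can see whether an event fades as the drug clears.

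**Conclusion.** The inconsistency is real and should be corrected. The two categories are not exhaustive, the Related list conflicts with the adverse-reaction threshold, and it also conflicts with Appendix 1's own references to ongoing related AEs and related deaths. The affected items are the treatment-related TEAE summaries, the two relatedness limbs of the halting rule, and unblinding for dose-escalation decisions.

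A reader might infer that the primary endpoint is compromised. It is not, because it counts AEs whatever their cause. A reader might also infer that the protocol intends to keep fatal or permanent events out of the Related category. The surrounding text shows the opposite intention, so the fault is in drafting.

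The size of any effect is unknown. The illustrative probabilities rest entirely on assumed event rates and classification rates, and an error could go in either direction. The conclusion rests on the literal wording and on the absence of a stated default, not on evidence of misclassification.

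**What to change.** Reconcile the two parts of Appendix 1 into one complementary pair based on the protocol's own threshold:

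- **Related:** a causal relationship with the product is at least a reasonable possibility.
- **Not Related:** there is no reasonable possibility of one.

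Keep timing, dechallenge, mechanism and rechallenge as matters to weigh, and say that they are not joint requirements. Carry the same wording into the eCRF guidance. Leave the halting thresholds in Section 3.7 as they are.

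State in the CSR which standard was applied to AEs already assessed, and resolve causality queries, including blank relationships, before unblinding. SAP Section 1 says that protocol Version 5 was never used for study conduct. The Version 4 to 5 change summary lists no change to the causality definitions, so the same wording appears to have applied under Version 4. If dosing is complete, the CSR statement and the blinded check are the practical route.

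The drafting cost is a few lines. The related-AE count may rise slightly. A change made partway leaves a mixed standard across cohorts unless earlier AEs get a blinded causality check. If dosing continues, the change may need a substantial amendment, because the definition feeds a safety halt.

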Appendix 2: Clinical Laboratory Evaluations

Clinical chemistry:	Haematology:	Urinalysis:
Alanine aminotransferase (ALT)	Haematocrit	Blood
Albumin	Haemoglobin	Glucose
Alkaline phosphatase (ALP)	Mean cell haemoglobin	Ketones
Aspartate aminotransferase (AST)	Mean cell haemoglobin concentration	pH
Calcium	Mean cell volume	Protein
Chloride	Platelet count	Specific gravity
Cholesterol	Red blood cell (RBC) count	Urobilinogen
Creatinine	White blood cell (WBC) count	Microscopic examination
Direct bilirubin	WBC differential:	
Gamma-glutamyl transferase (GGT)	Basophils	Coagulation profile:
Glucose	Eosinophils	Activated partial thromboplastin time (aPTT)
Inorganic phosphate	Lymphocytes	International normalized ratio (INR)
Potassium	Monocytes	Prothrombin time (PT)
Sodium	Neutrophils	
Total bilirubin		
Total CO ₂		
Total protein		
Uric acid		
Serology:^a	Drug screen:	Hormone panel - females only:
Anti-hepatitis B surface antibody	Including but not limited to:	Follicle-stimulating hormone (FSH) ^a
Hepatitis B surface antigen (HBsAg)	Amphetamines/methamphetamines	Serum pregnancy test (human chorionic gonadotropin) ^b
Hepatitis C antibody	Barbiturates	Urine pregnancy test ^b
Human immunodeficiency virus (HIV-1 and HIV-2) antibodies and p24 antigen	Benzodiazepines	
	Cocaine (metabolite)	
	Methadone	
	Phencyclidine	
	Opiates	
	Tetrahydrocannabinol/cannabinoids	Fasting Lipid Panel (Cohorts B4 onwards):
	Tricyclic antidepressants	Low-density lipoprotein cholesterol (LDL-c)
	Cotinine test	High-density lipoprotein cholesterol (HDL-c)
		Very low-density lipoprotein (VLDL)
		Total Cholesterol
		Triglycerides (TG)
		Apolipoprotein (Apo) A1
		ApoB
		ApoC3

a. Performed at screening only.

b. For all female subjects, performed in serum at screening and in urine at all other times. A positive urine pregnancy test will be confirmed with a serum pregnancy test.

Appendix 3: Total Blood Volume

Part A

The following blood volumes will be withdrawn for each subject:

	Volume per blood sample (mL)	Maximum number of blood samples	Total amount of blood (mL)
Clinical laboratory evaluations ^a	7.5	5	37.5
Serology	3.5	1	3.5
Coagulation	1.8	5	9.0
NST-6179 pharmacokinetics ^b	2.0	19	38.0
Pharmacogenomics ^c	6.0	1	6.0
Total:			94.0

Abbreviation: FSH = follicle-stimulating hormone.

a. Includes pregnancy and FSH tests.

b. Includes 3 additional samples that may be taken.

c. This is an optional sample, which may be collected with the subject's consent.

If extra blood samples are required, the maximum blood volume to be withdrawn per subject will not exceed 140 mL.

Part B

The following blood volumes will be withdrawn for each subject not participating in a group with metabolite identification:

	Volume per blood sample (mL)	Maximum number of blood samples	Total amount of blood (mL)
Clinical laboratory evaluations ^a	7.5	7	52.5
Serology	3.5	1	3.5
Coagulation	1.8	7	12.6
NST-6179 pharmacokinetics ^b	2.0	35	70.0
Pharmacogenomics ^c	6.0	1	6.0
Fasting lipid panel	2.5	3	7.5
Total:			152.1

Note: Increased dosing frequency may require 2 to 3 additional PK sample collections, however, the maximum blood volume collected will not exceed 190 mL.

Abbreviation: FSH = follicle-stimulating hormone; PK = pharmacokinetic(s).

a. Includes pregnancy and FSH tests.

b. Includes 3 additional samples (per PK sampling day) that may be taken.

c. This is an optional sample, which may be collected with the subject's consent.

If extra blood samples are required, the maximum blood volume to be withdrawn per subject will not exceed 190 mL.

The following blood volumes will be withdrawn for each subject participating in a group with metabolite identification:

	Volume per blood sample (mL)	Maximum number of blood samples	Total amount of blood (mL)
Clinical laboratory evaluations ^a	7.5	7	52.5
Serology	3.5	1	3.5
Coagulation	1.8	7	12.6
NST-6179 pharmacokinetics ^b	2.0	35	70.0
Metabolite identification ^b	2.0	35	70.0
Pharmacogenomics ^c	6.0	1	6.0
Total:			214.6

Abbreviation: FSH = follicle-stimulating hormone; PK = pharmacokinetic(s).

a. Includes pregnancy and FSH tests.

b. Includes 3 additional samples (per PK sampling day) that may be taken.

c. This is an optional sample, which may be collected with the subject's consent.

If extra blood samples are required, the maximum blood volume to be withdrawn per subject will not exceed 270 mL.

Appendix 4: Contraception Guidance

Definitions

Female of Childbearing Potential: premenopausal female who is anatomically and physiologically capable of becoming pregnant following menarche.

Female of Non-childbearing Potential:

1. **Surgically sterile:** female who is permanently sterile via hysterectomy, bilateral salpingectomy, and/or bilateral oophorectomy by reported medical history and/or medical records. Surgical sterilisation to have occurred a minimum of 6 weeks, or at the investigator's discretion, prior to screening.
2. **Postmenopausal:** females at least 45 years of age with amenorrhea for 12 months without an alternative medical reason with confirmatory follicle-stimulating hormone (FSH) level of ≥ 40 mIU/mL. The amenorrhea should not be induced by a medical condition such as anorexia nervosa, hypothyroid disease or polycystic ovarian disease, or by extreme exercise. It should not be due to concomitant medications that may have induced the amenorrhea such as oral contraceptives, hormones, gonadotropin-releasing hormones, anti-oestrogens, or selective oestrogen receptor modulators. Females on hormone replacement therapy with FSH levels < 40 mIU/mL may be included at the discretion of the investigator. Females aged > 60 years old whose FSH values are not ≥ 40 mIU/mL may be included at the discretion of the investigator and in consultation with the sponsor.

Fertile male: a male that is considered fertile after puberty.

Infertile male: permanently sterile male via bilateral orchiectomy.

Contraception Guidance

Female Subjects

Female subjects who are of non-childbearing potential will not be required to use contraception. Female subjects of childbearing potential must be willing to use 2 methods (1 primary and 1 secondary method) of birth control from the time of signing the informed consent form (ICF) until 90 days after the follow-up visit. Primary (non-barrier) methods of contraception include:

- hormonal injection (as prescribed)
- combined oral contraceptive pill or progestin/progestogen-only pill (as prescribed)
- combined hormonal patch (as prescribed)
- combined hormonal vaginal ring (as prescribed)
- surgical method performed at least 3 months prior to the screening visit:
 - bilateral tubal ligation

- Essure® (hysteroscopic bilateral tubal occlusion) with confirmation of occlusion of the fallopian tubes
- hormonal implant
- hormonal or non-hormonal intrauterine device (IUD)
- vasectomised male partner (sterilisation performed at least 90 days prior to the screening visit, with verbal confirmation of surgical success, and the sole partner for the female subject).

Secondary (barrier) methods of contraception include:

- male condom with spermicide
- female condom with spermicide
- over-the-counter sponge with spermicide
- cervical cap with spermicide (as prescribed)
- diaphragm with spermicide (as prescribed).

Female subjects of childbearing potential should refrain from donation of ova from check-in (Day -1) until 90 days after the follow-up visit.

Male Subjects

Male subjects (even with a history of vasectomy) with partners of childbearing potential must use a male barrier method of contraception (ie, male condom with spermicide) in addition to a second method of acceptable contraception from check-in until 90 days after the follow-up visit. Acceptable methods of contraception for female partners include:

- hormonal injection
- combined oral contraceptive pill or progestin/progestogen-only pill
- combined hormonal patch
- combined hormonal vaginal ring
- surgical method (bilateral tubal ligation or Essure® [hysteroscopic bilateral tubal occlusion])
- hormonal implant
- hormonal or non-hormonal IUD
- over-the-counter sponge with spermicide
- cervical cap with spermicide
- diaphragm with spermicide.

An acceptable second method of contraception for male subjects is vasectomy that has been performed at least 90 days prior to the screening visit, with verbal confirmation of surgical success.

For male subjects (even with a history of vasectomy), sexual intercourse with female partners who are pregnant or breastfeeding should be avoided unless condoms are used from the time of the first dose until 90 days after the follow-up visit. Male subjects are required to refrain from donation of sperm from check-in until 90 days after the follow-up visit.

Sexual Abstinence and Same-sex Relationships

Subjects who practice true abstinence, because of the subject's lifestyle choice (ie, the subject should not become abstinent just for the purpose of study participation), are exempt from contraceptive requirements. Periodic abstinence (eg, calendar, ovulation, symptothermal, postovulation methods) and withdrawal are not acceptable methods of contraception. If a subject who is abstinent at the time of signing the ICF becomes sexually active, they must agree to use contraception as described previously.

For subjects who are exclusively in same-sex relationships, contraceptive requirements do not apply. If a subject who is in a same-sex relationship at the time of signing the ICF becomes engaged in a heterosexual relationship, they must agree to use contraception as described previously.

